# 5.3. End of Study Visit:

Subjects will undergo an End of Treatment (EOT) Visit within 28 days of discontinuation of telaglenastat. The following EOT procedures are recommended:

- 1. AE monitoring
- 2. Recording of concomitant medications
- 3. Vital signs and weight
- 4. Complete physical examination
- 5. ECOG performance status evaluation

Protocol 2016-0636 Date: 06/03/2019

Page **22** of **39** 

- 6. Clinical laboratory values (hematology, chemistry)
- 7. Serum or urine pregnancy test for women of child-bearing potential
- 8. 12-lead ECG with QTcF
- 9. Bone marrow sample for biomarker and/or PDn analysis. This is only required if the reason for treatment discontinuation is relapse/disease progression following a PR or better. Patients with adequate numbers of leukemic blasts circulating in the peripheral blood may submit a whole blood sample instead of a bone marrow sample

# **5.4 Long Term Follow Up**

All patients discontinued from study treatment for any reason other than withdrawal of consent for treatment and follow-up will continue to be assessed for survival. Survival information (i.e. the date and cause of death) will be collected via quarterly telephone calls and/or clinical visits for a period of 5 years after the last subject has enrolled on the study.

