# 1.2 Secondary Objectives

The secondary objectives of the study are:

- 1.2.1. To explore the pharmacokinetics (PK) of telaglenastat in combination with AZA
- 1.2.2. To explore the pharmacodynamics (PDn) of telaglenastat in combination with AZA
- 1.2.3. To assess overall survival, event-free survival and duration of response of telaglenastat in combination with AZA

NCT ID: NCT03047993

Protocol 2016-0636 Date: 06/03/2019

Page **4** of **39** 

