#### 2. BACKGROUND AND SCIENTIFIC RATIONALE

## 2.1 Background

Myelodysplastic syndromes (MDS) are malignant clonal disorders characterized by ineffective hematopoiesis, bone marrow dysplasia, peripheral cytopenias including thrombocytopenia, and a propensity to transform into acute myeloid leukemia (AML).(1, 2) Classically, MDS is associated with apoptosis and excessive proliferation, resulting in a paradoxical combination of a hyper-cellular marrow and peripheral cytopenias.(3) The incidence of MDS in the United States is rising, with approximately 20,000 to 30,000 new cases of MDS diagnosed annually, and a median age at diagnosis of 70 years.(3, 4)

Over the past decade, clinical use of the hypomethylating agent azacitidine has been shown to improve patient quality of life, decrease transfusion requirements, and improve outcome parameters in MDS patients, and is now a standard of care for MDS patients requiring therapy. With current HMA regimens, achievement of an ORR is estimated at 28-70%, with a CR rate of only 6-34% in patients with MDS treated with front-line HMA therapy, and with a median length of response in the HMA-responders of only 8 to 10 months.(5-10)

MDS patients requiring therapy include those with intermediate-2 or High-risk disease by IPSS, or high or very-high risk by R-IPSS.(11) In addition, patients with otherwise intermediate MDS with high-risk molecular features including *TP53*, *ASXL1*, *EZH2*, and/or *RUNX1* mutations have been identified as a subgroup that may benefit from early therapeutic intervention.(12)

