### 4.2. Study Duration:

- 4.2.1. All subjects must complete a screening visit, day 1 visits for each new cycle, and an end-of-treatment visit.
- 4.2.2. Treatment will continue until discontinuation due to relapse, unacceptable toxicity, or disease progression as defined by the IWG 2006 criteria for MDS. This includes:
  - clinically significant progressive disease at any time, or

NCT ID: NCT03047993

Protocol 2016-0636 ate: 06/03/2019

Page **15** of **39** 

- a lack of clinical benefit after 5 cycles of treatment at the highest dose of study medication, or
- Possibility of undergoing allogeneic stem cell transplantation
- discontinuation of study drug for more than 6 weeks, or
- intercurrent illness that prevents further administration of treatment, or
- unacceptable adverse event(s), or
- patient decision for study withdrawal, or
- general or specific changes in the patient's condition that render the patient unacceptable for further treatment in the judgment of the investigator

Patients may remain on study for up to 12 cycles if the patient demonstrates clinical benefit and no excessive toxicity (i.e. no clinically significant study-drug related grade  $\geq$  3 toxicity). Patients who are experiencing clinical benefit and have not experienced excessive toxicity may be eligible to continue therapy after discussion with the PI and the discussion documented in the patient's medical record.

If one of the study agents is discontinued due to toxicity, the patient may remain on study until the occurrence of significant disease progression, severe toxicity that requires all study agents to be permanently discontinued, or at the discretion of the PI.

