#### 5.2.3. Cycle 1 Day 8, Day 15, Day 22 (+/- 3 days)

At these Cycle 1 mid-cycle assessments, patients will return to clinic to undergo the following procedures:

NCT ID: NCT03047993

Protocol 2016-0636 ate: 06/03/2019 Version 1

Page **21** of **39** 

- 1. AE monitoring
- 2. Recording of concomitant medications
- 3. Vital signs and weight
- 4. Symptom-directed physical exam
- 5. Clinical laboratory evaluation (hematology, serum chemistries)
- 6. Plasma samples for PK analysis pre-dose on C1D15
- \*Patients may take their telaglenastat doses prior to, during, or after their clinic visit according to their usual dosing schedule because there are no specified pre-dose procedures *with the exception of C1D15* where the patient should not take their telaglenastat dose prior to arrival due to pre-dose PK sample.

## 5.2.4. Cycle 2 Day 1 (+/- 5 days) and all subsequent cycles on Day 1

Patients may take their telaglenastat doses prior to, during, or after their clinic visit according to their usual dosing schedule because there are no specified pre-dose study procedures *with the exception of C2D1 and C3D1* due to pre-dose PK samples.

- 1. Vital signs and weight
- 2. AE monitoring
- 3. Recording of concomitant medications
- 4. Symptom-directed physical exam
- 5. Clinical laboratory values (hematology, serum chemistry)
- 6. Plasma sample for exploratory biomarker analysis
- 7. Bone marrow evaluation of tumor/disease burden is required for all patients receiving telaglenastat on cycle 2 day 1, cycle 4 day 1, cycle 6 day 1, and every 3 cycles thereafter, +/- 5 days for all above assessments. Additional evaluations are acceptable as clinically indicated.
- 8. Bone marrow sample for biomarker and pharmacodynamics analysis during above protocol-defined time points.
- 9. Plasma samples for correlative analysis on same day as bone marrow sample timepoints are collected
- 10. Plasma samples for PK analysis prior to the administration of study drug, on C2D1 and C3D1.

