# Response criteria (Responses must last at least 8 weeks)†

Hgb increase by ≥1.5 g/dL Relevant reduction of units of RBC transfusions by an absolute number of at least 4 RBC transfusions/8 wk compared with the pretreatment transfusion number in the previous 8 wk. Only RBC transfusions given for a Hgb of ≤9.0 g/dL pretreatment will count in the RBC transfusion response evaluation†

Absolute increase of ≥30 × 109/L for patients starting with >20 × 109/L platelets Increase from <20 × 109/L to >20 × 109/L and by at least 100%† At least 100% increase and an absolute

increase >0.5 × 109/L† At least 1 of the following:

At least 50% decrement from maximum response levels in granulocytes or platelets

Reduction in Hgb by > 1.5 g/dL Transfusion dependence

Source: (Cheson, et al. 2006) Abbreviations: Hgb indicates hemoglobin; RBC: red blood cell; HI: hematologic improvement. Note: Deletions to the IWG response criteria are not shown. Note: To convert hemoglobin from g/L to g/dL, divide g/L by 10. \*Pretreatment counts averages of at least 2 measurements (not influenced by transfusions) ≥1 week apart (modification).

†Modification to IWG response criteria (Cheson, et al. 2003) ‡In the absence of another explanation, such as acute infection, repeated courses of chemotherapy (modification), gastrointestinal bleeding, hemolysis, and so forth.

For each subject, response to therapy, duration of response, event-free survival, and overall survival will be calculated. The duration of response is defined as the number of

\*Responses must last at least 8 weeks

NCT ID: NCT03047993 Protocol 2016-063 Date: 06/03/2019

Page **25** of **39** 

days from the date of initial response (PR or better) to the date of first documented disease progression/relapse or death, whichever occurs first. Event-free survival is defined as the number of days from the date of treatment initiation (i.e., C1D1) to the date of documented treatment failure, relapses from CR, or death from any cause, whichever occurs first, and will be calculated for all patients. In the event that neither disease progression or death is documented prior to study termination, analysis cutoff, or the start of confounding anticancer therapy, these endpoints will be censored at the

In addition, relationships between anti-tumor activity, PDn markers, exploratory biomarkers, and drug exposure levels will be explored.

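### Relapse after an event-free stop of treatment is not collected, so duration of response, and possibly event-free survival, will tend to be reported too long

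*Combined protocol and SAP*

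**What the plan says.** Section 1.2, objective 1.2.3, is "To assess overall survival, event-free survival and duration of response of telaglenastat in combination with AZA". Section 6.2.2, after the hematologic improvement criteria, measures DoR in "days from the date of initial response (PR or better) to the date of first documented disease progression/relapse or death, whichever occurs first". EFS runs from C1D1 to documented failure, relapse from CR or death, and is calculated for all patients. Neither definition is limited to time on treatment. Where no progression or death is documented before study termination, analysis cutoff or the start of confounding anticancer therapy, the patient is censored at the last tumor assessment. Section 8.3 estimates EFS, DoR and overall survival by Kaplan-Meier.

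Disease assessment is tied to treatment. Section 5.2.4 states: "Bone marrow evaluation of tumor/disease burden is required for all patients receiving telaglenastat", at C2D1, C4D1, C6D1 and every 3 cycles after that. Section 5.3 adds one end-of-treatment visit. A marrow sample is required there only when the reason for stopping is relapse or progression after PR or better. Section 5.4 then says that patients off treatment "will continue to be assessed for survival. Survival information (i.e. the date and cause of death) will be collected via quarterly telephone calls". Contacts run until 5 years from the last enrolment. The clinical-visit option in the same sentence changes the route of contact but not the data collected.

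Section 4.2.2 allows treatment to end without an EFS or DoR event, for example for transplant, toxicity, intercurrent illness or the patient's own decision. It also says: "Patients may remain on study for up to 12 cycles if the patient demonstrates clinical benefit and no excessive toxicity", with continuation possible after discussion with the PI.

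**The concern.** DoR and EFS need a relapse or progression date whenever it occurs, but the plan stops looking for one when treatment stops. A responder who leaves treatment in remission, relapses later and then dies enters the DoR curve at the date of death. Another responder with the same course who is still alive at cutoff is censored back at the last on-treatment assessment. The curve thus mixes relapse times with later death times, and which one a patient contributes depends on why treatment stopped and whether a death was reported.

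The rule for new therapy would limit this, but it needs a start date that Section 5.4 does not list. If that date is unknown, the patient is scored as if no new therapy had been given.

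The background in Section 2.1 sets the comparison that readers will make, describing current treatment "with a median length of response in the HMA-responders of only 8 to 10 months". A DoR somewhat above that range could come from how follow-up is collected rather than from the combination.

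**Working it through.** **1. The plan's own figures.** The documents size nothing on EFS or DoR. The only design figures are those of the Simon design in Section 8.1.2 (stop at 6 or fewer of 16; success at 15 or more of 28). Exact binomial calculation gives:
- P(stop early | 40%) = P(X ≤ 6; n = 16, p = 0.40) = 0.527
- expected N = 16 + (1 − 0.527) × 12 = 21.7
- type I error 0.0989 and power 0.803

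The stated 53% and 22 reproduce. They concern response within the first 6 cycles and are not touched by this point.

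**2. One history under the plan's rules.** Illustrative times in months from first response: stops event-free at 5, relapses at 9, dies at 15. True DoR is 9.

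| What is known | Plan's DoR |
|---|---|
| Death documented, no new therapy | event at 15 |
| Alive at cutoff | censored at last assessment, about 5 |
| New therapy begun before death, start date known | censored at last assessment, about 5 |
| New therapy begun before death, start date not collected | event at 15 |

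No row gives the true value of 9.

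**3. How much relapse falls inside scheduled assessment.** Twelve cycles are 12 × 28 = 336 days. The window after first response is w = (336 − onset day)/30.44 months. With exponential relapse at a 9-month median (midpoint of the 8 to 10 in Section 2.1), P(relapse inside) = 1 − 2^(−w/9).

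| First response | Day | w (months) | P(inside) |
|---|---|---|---|
| C2D1 | 29 | 10.1 | 54% |
| C4D1 | 85 | 8.2 | 47% |
| C6D1 | 141 | 6.4 | 39% |

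These apply only if treatment ends at 12 cycles.

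**4. Effect on median DoR, by simulation.** Assumptions not in the documents: true median 9.0 months; onset split 40/40/20% over the three marrows; monthly hazard 2 to 8% of stopping without relapse; median 6 to 12 months from relapse to death; deaths followed to 36 months. New-therapy censoring is non-informative by construction.

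| Scenario | Median DoR under the plan | Responders with a recorded relapse |
|---|---|---|
| All stop at 12 cycles, none censored for new therapy | 11.3–13.6 | 36–45% |
| All stop at 12 cycles, half of event-free stoppers censored for new therapy | 9.9–11.8 | 36–45% |
| May continue past 12 cycles, 0 to 80% of event-free stoppers censored for new therapy | 9.1–11.6 | 49–80% |

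**5. A second calculation, on the curve.** Assumptions: response at about month 2, hard stop at 12 cycles, 0, 25 or 50% of responders stopping earlier without relapse, median 6 or 12 months from relapse to death, no new-therapy censoring. Probability of still being in response:

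| True median | 12 months: true → with death dates | 18 months: true → with death dates |
|---|---|---|
| 8 | 0.35 → 0.44–0.53 | 0.21 → 0.35–0.45 |
| 10 | 0.44 → 0.52–0.60 | 0.29 → 0.43–0.53 |

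The excess is about 0.08 to 0.18 at 12 months and 0.14 to 0.24 at 18 months. The median moves by 0 to about 10 months. It does not move when the true median is 8 and nobody stops early, because half the relapses then fall before the stop. These are upper scenarios, because of the hard stop and the absence of new-therapy censoring.

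**The case against.** A reader might infer that relapse and progression dates are lost for the trial as a whole. The documents do not support that. A patient who stops because of relapse, progression or failure has the event documented at or before stopping, so the gap is confined to patients who stop event-free.

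A reader might also take the 13.6-month figure as the expected result. It requires every responder to stop at 12 cycles, whereas Section 4.2.2 lets patients with benefit and no excessive toxicity continue after discussion with the PI, and responders are the natural candidates. It also requires that no one is censored for new therapy, although Section 6.2.2 provides for this. Both objections stand, and they bring the range down to about 9 to 11.6. The second stands only in part, because Section 5.4 does not collect the date the rule needs, and Section 6.2.2 does not say whether transplant counts as confounding therapy.

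Nor is an EFS bias of known size supported. EFS includes all patients, failure in non-responders would usually be documented on treatment, and the calculations cover DoR only.

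Finally, these endpoints are secondary and mainly descriptive. Section 8.3 plans log-rank comparisons among subgroups, but no test against 8 to 10 months. Sampling error is large: assuming 15 responders with complete follow-up, a true 9-month median would be estimated anywhere from about 4 to 17 months (95% range). That limits the consequence, but a systematic shift adds to sampling error and the confidence interval does not show it.

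**Conclusion.** The concern holds for patients who stop study treatment without relapse, progression or failure. For them the plan collects only date and cause of death, while DoR and EFS continue past treatment. It also cannot reliably apply its own new-therapy censoring rule. In the settings examined, dating such events at death did not shorten DoR and usually lengthened it.

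For a true median of 9 months, the reported median would be about 9 to 11.6 months if responders may continue past 12 cycles. The upper scenario, with a hard stop and no new-therapy censoring, reaches about 13.6. These figures rest on assumed rates of event-free stopping, survival after relapse and exponential times, none of which the documents give. An effect on EFS is possible but not quantified. The primary response endpoint and the Simon design are unaffected.

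**What to change.** - **Section 5.4:** for patients who stop event-free, also record at the planned quarterly contacts the date of any relapse or progression, from routine counts and marrows, and the start date of any new anticancer therapy or transplant. Continue until the first such event.
- **Section 6.2.2:** date EFS and DoR events from these records, and apply the existing new-therapy censoring rule with the collected start date. State whether transplant counts as confounding therapy.
- **Section 8.3:** add a sensitivity analysis that censors event-free stoppers at the last disease assessment instead of counting a death after a gap in disease follow-up. Whether to count such deaths is a debatable choice of estimand, so this belongs beside the main analysis rather than in place of it.

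If the extra collection is declined, the minimum is to state that EFS and DoR are censored at the last disease assessment for event-free stoppers, with a sensitivity analysis.

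Cost: a paragraph in 5.4, short additions to 6.2.2 and 8.3, and a few follow-up CRF fields. No new visits or marrows are needed. The relapse criteria use counts, marrow or transfusion data, so a telephone contact will sometimes mean retrieving outside records. The reported DoR may be shorter.

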#### 6. RESPONSE DEFINITIONS

### **6.1 Study Endpoints:**

**6.2.1. Efficacy Analysis:** Clinical activity of telaglenastat + AZA will be assessed based on Modified IWG Response Criteria for MDS (Cheson et al, 2006).

Proposed Modified International Working Group Response Criteria for Altering Natural History of MDS Category	Response criteria (Responses must last at least 4 weeks)
Complete remission	Bone marrow: ≤5% myeloblasts with normal maturation of all cell lines* Persistent dysplasia will be noted*† Peripheral blood‡ Hgb ≥11 g/dL Platelets ≥100 × 109/L Neutrophils ≥1.0 × 109/L† Blasts = 0%
Partial remission	All CR criteria if abnormal before treatment except: Bone marrow blasts decreased by ≥50% over pretreatment but still >5% Cellularity and morphology not relevant
Marrow CR†	Bone marrow: ≤5% myeloblasts and decrease by ≥50% over pretreatment† Peripheral blood: if HI responses, they will be noted in addition to marrow CR†
Stable disease	Failure to achieve at least PR, but no evidence of progression for >8 wks

Protocol 2016-0636 Date: 06/03/2019

Page **23** of **39** 

Failure Death during treatment or disease

progression characterized by worsening of cytopenias, increase in percentage of bone marrow blasts, or progression to a more advanced MDS FAB subtype than

pretreatment

Relapse after CR or PR At least 1 of the following: Return to

pretreatment bone marrow blast percentage Decrement of ≥50% from maximum remission/response levels in granulocytes or platelets Reduction in Hgb concentration by ≥1.5 g/dL or

transfusion dependence

Cytogenetic response Complete: Disappearance of the

chromosomal abnormality without

appearance of new ones Partial: At least

50% reduction of the chromosomal

abnormality

Disease progression For patients with: Less than 5% blasts:

≥50% increase in blasts to >5% blasts 5%-10% blasts: ≥50% increase to >10% blasts 10%-20% blasts: ≥50% increase to >20% blasts 20%-30% blasts: ≥50%

increase to >30% blasts

Any of the following: At least 50%

decrement from maximum

remission/response in granulocytes or platelets Reduction in Hgb by ≥2 g/dL

Transfusion dependence

Survival Endpoints: Overall: death from any cause

Event free: failure or death from any cause PFS: disease progression or death from MDS DFS: time to relapse Cause-specific death: death related to MDS

Source: (Cheson, et al. 2006) Abbreviations: MDS = myelodysplastic syndromes; CR = complete remission; Hgb = hemoglobin; HI = hematologic improvement; PR = partial remission; FAB = French-American-British; AML = acute myeloid leukemia; PFS = progression-free survival; DFS = disease-free survival. Note: Deletions to IWG response criteria are not shown. Note: To convert hemoglobin from g/L to g/dL, divide g/L by 10. \*Dysplastic changes should consider the normal range of dysplastic changes (modification).

†Modification to IWG response criteria (Cheson, et al. 2003) ‡In some circumstances, protocol therapy may require the initiation of further treatment (e.g., consolidation, maintenance) before the 4-week period. Such subjects can be included in the response category into which they fit at the time the therapy is started. Transient

Protocol 2016-0636 Date: 06/03/2019

Page **24** of **39** 

cytopenias during repeated chemotherapy courses should not be considered as interrupting durability of response, as long as they recover to the improved counts of the previous course.

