#### 3. STUDY ELIGIBILITY

#### 3.1 Inclusion Criteria

- 1. Signed, informed consent must be obtained prior to any study specific procedures.
- 2. Subjects must be ≥ 18 years of age at the time of informed consent
- 3. Subjects with a histologically confirmed diagnosis of MDS, including both MDS and RAEB-T (AML with 20-30% blasts and multilineage dysplasia by FAB criteria) by World Health Organization (WHO) and chronic myelomonocytic leukemia (CMML) are eligible.
- 4. Subjects with high-risk MDS (i.e. IPSS Intermediate-2 or high-risk; or R-IPSS high or very-high risk). Patients with Intermediate-1 risk by IPSS or Intermediate risk by R-IPSS and with IDH1 or IDH2, or high-risk molecular features including TP53, ASXL1, EZH2, and/or RUNX1 mutations are also eligible.
- 5. Subjects with prior hypomethylating agent therapy exposure may be eligible based on discussion with the PI.
- 6. Eastern Cooperative Oncology Group (ECOG) Performance Status of 0-2.
- 7. Adequate liver function, as evidenced by a serum bilirubin < 2x the ULN (except for patients with Gilbert's disease) and ALT or AST < 3x the laboratory ULN.
- 8. Adequate renal function including creatinine clearance > 30 mL/min based on the Cockcroft-Gault equation.
- Able to understand and voluntarily sign a written informed consent, and willing and able to comply with protocol requirements.
- 10. Resolution of all clinically significant treatment-related, non-hematological toxicities, except alopecia, from any previous cancer therapy to < Grade 1 prior to the first dose of study treatment

Protocol 2016-0636 ate: 06/03/2019

Page **12** of **39** 

11. Female patients of childbearing potential must have a negative serum or urine pregnancy test within 3 days of the first dose of study drug and agree to use dual methods of contraception during the study and for a minimum of 3 months following the last dose of study drug. Post-menopausal females (> 45 years old and without menses for > 1 year) and surgically sterilized females are exempt from these requirements. Male patients must use an effective barrier method of contraception during the study and for a minimum of 3 months following the last dose of study drug if sexually active with a female of childbearing potential.

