#### 8.1.2. Phase II:

The Simon minimax two-stage design will be employed for the Phase II portion.(15) We assume a target response rate of 60% and a response rate of 40% or lower will be considered not desirable. Response is defined as complete remission (CR), partial remission (PR), marrow CR (mCR), or Hematologic Improvement (HI) by modified IWG criteria for MDS patients. For example a 29% CR/PR rate was reported in the azacitidine arm in the randomized AZA-001 trial, and a 23% CR/PR rate and 60% ORR (including 37% HI) was seen in the azacitidine arm of the CALGB 9221 trial. To implement the Simon's two-stage design, the assessment window for response (CR+PR+mCR+HI) is defined as response occurring within the first 6 cycles of treatment. With a type I error rate of 10% and 80% power, we will enroll 16 patients in the first stage. If 6 or fewer patients achieve response, enrollment will be halted. If 7 or more out of the first 16 patients achieve response, accrual will continue until a total of 28 patients have been enrolled. If 15 or more out of these 28 patients achieve response, the treatment will be considered efficacious and worthy of further investigation. Under this Simon's minimax two-stage design, the probability of early termination is 53% and the expected sample size is 22 if the true response rate is 40%.

Protocol 2016-0636 Date: 06/03/2019

Page **34** of **39** 

A Toxicity Summary will be submitted to the IND Office Medical Monitor after the first 7 evaluable patients and every 7 evaluable patients thereafter.

A Response Summary will be submitted to the IND Office Medical Monitor after 15 evaluable patients complete 6 cycles of study treatment.

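### Marrow CR counts alone as a primary response with no minimum pretreatment blast level, so a patient starting at or below 5% blasts can be scored a responder by halving a very small percentage, provided the 4-week duration rule is met

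*Combined protocol and SAP*

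**What the plan says.** Section 6.2.1 assesses activity by the modified IWG 2006 criteria. In the table, the marrow CR row reads "Bone marrow: ≤5% myeloblasts and decrease by ≥50% over pretreatment". On blood counts it says only "if HI responses, they will be noted in addition to marrow CR", so hematologic improvement (HI) is recorded but not required. The column header applies a duration rule to every row: "Response criteria (Responses must last at least 4 weeks".

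Section 8.1.2 sets the primary endpoint: "Response is defined as complete remission (CR), partial remission (PR), marrow CR (mCR), or Hematologic Improvement (HI) by modified IWG criteria for MDS patients". Marrow CR therefore counts by itself toward the rules of at least 7 of 16 and at least 15 of 28. Section 8.3 uses the same composite.

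Eligibility in Section 3.1, item 4, goes by risk score: "Subjects with high-risk MDS (i.e. IPSS Intermediate-2 or high-risk; or R-IPSS high or very-high risk". It adds a second route: "Patients with Intermediate-1 risk by IPSS or Intermediate risk by R-IPSS and with IDH1 or IDH2, or high-risk molecular features". Neither Section 3.1 nor Section 3.2 sets a minimum marrow blast percentage.

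Section 5.2.4 schedules marrows on day 1 of cycles 2, 4 and 6, then every third cycle. The response window in Section 8.1.2 is the first 6 cycles.

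**The concern.** In a patient with 10% blasts, reaching 5% or less after at least a halving is a visible change in the disease. In a patient with 2%, the 5% condition is already met at baseline, and the halving amounts to one percentage point, within reach of counting error.

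The other components have safeguards that marrow CR lacks. Each HI category in Section 6.2.2 requires an abnormal pretreatment count. CR demands hemoglobin, platelet and neutrophil thresholds. PR requires blasts that are halved but still above 5%. Marrow CR has neither a baseline condition nor a blood-count condition.

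Any such false responses can only raise the observed rate, and they enter both decision points of a design with almost no slack in its 10% type I error. The azacitidine rates cited in Section 8.1.2 (29% CR/PR; 23% CR/PR with 37% HI) show no marrow CR component, so the 40% null rate is not shown to allow for them.

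**Working it through.** **1. The plan's own design.** Inputs from Section 8.1.2: null rate 40%, target 60%, stop at 6 or fewer of 16, success at 15 or more of 28. With X1 ~ Bin(16, p) and X2 ~ Bin(12, p):

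- P(early stop) = P(X1 ≤ 6) = 0.527 at p = 0.40 (stated 53%).
- Expected N = 16 + (1 − 0.527) × 12 = 21.7 (stated 22).
- P(go) = Σ over x ≥ 7 of P(X1 = x) × P(X2 ≥ 15 − x) = 0.0989 at p = 0.40 and 0.803 at p = 0.60 (stated limits 10% and 80%).

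The design reproduces. The issue lies in what is counted, not in the Simon arithmetic.

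**2. Does 2% to 1% qualify?** The final value of 1% is at most 5%, and (2 − 1)/2 = 50%. Both marrow CR conditions are met. What remains is the 4-week rule.

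**3. How would 4 weeks be shown?** Marrows on day 1 of cycles 2, 4 and 6 are two 28-day cycles (8 weeks) apart, and no confirmatory marrow is specified. Two readings are therefore computed: two consecutive qualifying marrows, or any one of the three.

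**4. Counting noise with no true change.** Assumptions not in the documents: true blast fraction q constant, binomial counting error, and m = 200 or 500 cells. Let x be the baseline count, restricted to x > 0 and x/m ≤ 5%. The chance that one follow-up count is at most half of x is h(x) = P(Y ≤ x/2), with Y ~ Bin(m, q). Averaging over x:

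- one given marrow: mean of h
- any of three: mean of 1 − (1 − h)³
- two consecutive of three: mean of 2h² − h³

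| True blasts | One marrow, 200 / 500 cells | Any of three | Two consecutive |
|---|---|---|---|
| 1% | 37% / 18% | 68% / 41% | 25% / 9% |
| 2% | 22% / 8% | 47% / 21% | 12% / 3% |
| 3% | 14% / 4% | 33% / 10% | 5% / 0.7% |
| 4% | 7% / 1% | 19% / 3% | 1.4% / 0.05% |
| 5% | 3% / 0.1% | 8% / 0.4% | 0.2% / about 0 |

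**5. Effect on the decision.** Let f be the share of patients at or below 5% (not given) and e the chance that a low-blast non-responder is falsely scored. The apparent rate at a true 40% is p = 0.40 + f × 0.60 × e. For example, f = 0.25 and e = 0.12 give 0.40 + 0.018 = 0.418. Putting p into the P(go) formula of step 1:

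| f | e | Apparent rate | P(go) |
|---|---|---|---|
| 0 | 0 | 0.400 | 9.9% |
| 10% | 1% | 0.4006 | 10.0% |
| 10% | 12% | 0.4072 | 11.3% |
| 25% | 1% | 0.4015 | 10.2% |
| 25% | 12% | 0.418 | 13.8% |

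The range of e from 1% to 12% spans most of the two-consecutive column for patients at 2% to 4%. A group made up entirely of patients at 1% would exceed it with 200 cells.

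**The case against.** The plan names a published standard and uses its marrow CR definition consistently in Sections 6.2.1, 8.1.2 and 8.3. Nothing is miscopied or contradictory, and a trial-specific restriction costs some comparability with studies that use the same criteria. That stands. It is why the published-criteria rate should be reported as well, but it does not remove the upward bias.

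The population is advanced MDS, mostly higher-risk, so few patients may start at or below 5%. This also stands: the documents give no share. A reader might take the progression row for patients with under 5% blasts ("For patients with: Less than 5% blasts") as proof that the trial expects them. It is not, because that row belongs to a general-purpose published table. The better evidence is that Sections 3.1 and 3.2 set no floor and that intermediate-risk patients can enter on mutation status.

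A reader might also infer that any single 2% to 1% reading is scored as a response, and that the false-go chance is 11-19% or more. The 4-week header does not support the first inference. The second needs 5-25% of low-blast non-responders to be falsely scored at a 25% share (p = 0.4075 to 0.4375, P(go) 11.4% to 18.9%). Under counting noise alone, that means either that a second marrow is not required or that blasts sit near 1%. The duration rule is not airtight, however: no confirmatory marrow is named, and a table footnote lets a response stand if protocol therapy requires further treatment before 4 weeks.

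**Conclusion.** The gap in the definition is certain from the text: no blast minimum for marrow CR, none for eligibility, and marrow CR sufficient by itself for the primary response. Followed as written, the plan can score a response in a patient who was never above 5%, provided the change meets the 4-week rule.

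The size is modest and rests on assumptions. If duration takes two consecutive marrows, the false-go chance at a true 40% rate moves from 9.9% to about 10-14% with a 25% low-blast share, and to about 10-11% with a 10% share. It could be larger if a single marrow were accepted. The low-blast share, the cells counted and the false-scoring rate are all assumed; the documents give none of them. This is a worthwhile, inexpensive improvement to the endpoint. It does not show that the design fails or that its operating characteristics are wrong.

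**What to change.** Add to Sections 6.2.1 and 8.1.2: *Marrow CR counts toward the primary response only in patients with pretreatment marrow blasts above 5%. Patients at or below 5% can respond by CR or HI. All evaluable patients remain in the denominator.*

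Add to Section 8.3 that the response rate will also be reported under the IWG criteria as published, and by baseline blasts (above 5%; 5% or below). State in Section 6.2.1 what evidence satisfies the 4-week rule for marrow CR, since this decides which column of the noise table applies.

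The cost is a few sentences. Baseline marrow is already required at screening (Table 2 of Section 5.1), and the sample size and both cut-offs are unchanged. The downsides are a slightly lower response rate and a small departure from the cited table, which reporting the as-published rate offsets.
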